## 9.5 Planned subgroup analyses

For the statistical analyses of the subgroups, the models defined in the sections above will be used for the respective outcome, additionally with an interaction term of the treatment group variable with the subgroup, in order to obtain indications of differential treatment effects in the subgroups. We will report effect estimates of interaction effects with corresponding 95%CI. In addition, marginal effect estimates for each subgroup and 95% confidence intervals will be provided.

| Sub-group (levels)                     | Outcomes  |
|--|---|
| Sex (male, female, diverse)     | Primary endpoint and efficacy related secondary endpoints |
| Age
(< 40 years, ≥ 40 years) | Primary endpoint and efficacy related secondary endpoints |

| Sub-group (levels)  | Outcomes  |
|---|---|
| Education (higher education meaning A-levels or higher, medium or lower educational achievement)   | Primary endpoint and efficacy related secondary endpoints   |
| Employment status
(retired/ currently unable to work, employed/ self-employed endpoints / student)  | Primary endpoint and efficacy related secondary endpoints   |
| Body-mass index (BMI)
( $< 30 \text{ kg}^* \text{m}^{-2}$ , $\geq 30 \text{ kg}^* \text{m}^{-2}$ )  | Primary endpoint and efficacy related secondary endpoints   |
| ME/CFS vs. Post-COVID-ME/CFS   | Primary endpoint and efficacy related secondary endpoints, OCT outcome: Retinal vascular and perfusion density in the superficial vascular plexus (SVP) |
| Disease duration
( $\leq 2.5$ years, $> 2.5$ years)   | Primary endpoint and efficacy related secondary endpoints   |
| Bell Score at baseline
( $\leq 30$ , $> 30$ )   | Primary endpoint and efficacy related secondary endpoints   |
| Chalder Fatigue Scale at baseline
( $\leq 20$ , $> 20$ )  | Primary endpoint and efficacy related secondary endpoints   |
| Focal neurological deficit at baseline (yes, no)   | Primary endpoint and efficacy related secondary endpoints   |
| Antineuronal autoantibodies (yes, no)  | Primary endpoint and efficacy related secondary endpoints   |
| Subgroups by 7 PROMIS 29 sub domains (T-score cut offs of 30-40)   | Primary endpoint and efficacy related secondary endpoints   |
| Baseline detection of GPCR-Autoantibodies (pos. result from Labor Celltrend; yes, no)  | Primary endpoint and efficacy related secondary endpoints   |
| Subgroups by the presence of specific B-cell subpopulations at baseline (incl. activated plasma blasts, memory like and activated naïve like cells identified in CyTOF analysis) | Primary endpoint and efficacy related secondary endpoints   |
| Subgroups by baseline retinal nerve fibre layer (pRNFL) thickness (median split)   | Primary endpoint and efficacy related secondary endpoints   |

| Sub-group (levels)  | Outcomes  |
|---|---|
| Subgroups by baseline retinal ganglion cell layer (GCIPL) thickness (median split) | Primary endpoint and efficacy related secondary endpoints |

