## 4.2 Power consideration

In this study, a total of 66 patients (allocated in a 2:1 ratio: immunoabsorption (IA) group: 44 patients vs. sham group: 22 patients) will be included. Limited data from 2 small pilot studies, investigating IA in 10 patients with CFS/ME, is available to date. Consequently, data is lacking about precise effects, clinical outcomes, and effect sizes in this group of patients.

The justification of the sample size is based on the primary endpoint (change from baseline of the Chalder Fatigue Scale). The Chalder Fatigue Scale measures fatigue in patients using the overall score (range from 0 to 33) derived from a questionnaire with 11 questions (each scored from 0 to 3, see (Cella & Chalder, 2010; Chalder et al., 1993) for more details). Based on Cella & Chalder 2010, the mean score in a population of patients

suffering from CFS is 24.4 (with a standard deviation of 5.8) and for a healthy sample a mean value of 14.2 (with a standard deviation of 4.6) was observed. A difference of 10 points cannot be expected in this study since only patients suffering from CFS are included. In the systematic review of Nordin et al. 2016 a minimal important difference for the global change ranges between 2.3 and 3.3.

In an earlier study (Cleare et al. 1999) examining the efficacy of various treatments for CFS/ME, the difference in means of the Chalder Fatigue Scale was 4.5 points (Likert score) between the active and the control group. However, no sham-controlled study evaluating the effect of IA on CFS/ME has been conducted so far, but first pilot studies suggest a positive effect of IA in patients with CFS/ME.

To explore the expected precision obtained from the planned study, the distance from the mean group difference of the primary endpoint (change from baseline in Chalder Fatigue Scale) to the limits is calculated using its 95% confidence interval (CI) and a common standard deviation of 5.8 as provided for patient with CFS/ME in (Cella & Chalder, 2010). Using these assumptions and the given group sample sizes of 44 patients and 22 patients, the distance from mean to the limits of the 95%-CI is 3.03 points in the Chalder Fatigue Scale. Assuming an expected drop-out rate of 20% (resulting in expected group sample sizes of 35 and 18 patients, respectively) the distance from the mean to the limits of the 95%-CI increases to 3.37 points in the Chalder Fatigue Scale.

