| Schellong Test /POTS   | pst_0021-pst_0080  | Using items to evaluate if POTS is present (Increase in heart rate within 10 minutes of standing by at least 30 beats/minute above the level when lying down or, to at least 120 beats/minute absolutely, no pathological drop in blood pressure (i.e., systolic drop not more than 20 mm Hg and diastolic drop not more than 10 mm Hg), increasing symptoms of orthostatic intolerance) |
| 6 Minute Walking Test (6 MWT)  |  |  |
| MoCA   | moca_0011-moca_0110  | Score items, sum of maximum 30 or 31 points dependent on educational level   |
| Symbol Digit Modalities Test, SDMT   | sdmt_0020  | Item on number of correct remembered words after 90 seconds  |
| PROMIS-29, physical function, anxiety, depression, pain interference, pain severity, fatigue, sleep disturbance, ability to participate in social roles and activities | pfa11-pfa53, edanx01-edanx53, eddep04-eddep41, hi7, an3, fatexp41, fatexp40, sleep109, sleep116, sleep20, sleep44, srpper11_caps-srpper46_caps, pain9-pain34, global07 | each of the 7 domains will be scored separately, transformation in standardized t-values   |
| PROMIS cognitive function short form 4a  | pc2r-pc42r   | Sum score converted to t score   |
| Additional secondary outcome variables   |  |  |
| VLMT (verbal learning and memory test)   | vlmt_0011 – vlmt_0220  | total score : addition of the learning achievements of the 5  |

|   |                       |   |
|---|-----------------------|---|
|   |                       | rounds; delayed recall : number of words correctly recalled from the word list after a time delay; loss after delay : subtraction of the number of correctly recalled words in learning session 7 from the number of correctly recalled words in learning session 5; correct recognition : subtraction of the number of false positives and interference items from the number of correctly recognised words in the first list (i.e.: 18. recognition performance (W) - (19. interference + 20. false positives)). |
| BVMT-R (brief visuospatial memory test revised) | bmvt_0011 – bmvt_0150 | total score : addition of the points from all three trials; delayed recall : number of correctly remembered figures. (correct figure and correct place); percent retained : [delayed recall / (higher of trial 2 and trial 3)] x 100; recognition discrimination index : (recognition hits) - (recognition false alarms)  |

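### SAP 9.5 sets one undirected T-score range (30-40) for all seven PROMIS-29 domains, which is the low-symptom tail for five of them and leaves the fatigue subgroup almost empty on that side

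*SAP*

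**What the plan says.** The PROMIS row of the subgroup table in SAP section 9.5 gives a single bracketed specification for all seven domains: "T-score cut offs of 30-40". It does not say which value in the range is the cut, how many groups result, or which side counts as impaired. The row applies to the primary endpoint and to the efficacy-related secondary endpoints.

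For each subgroup the outcome model is refitted "additionally with an interaction term of the treatment group variable with the subgroup", and marginal effects with 95% confidence intervals are reported within each subgroup.

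Table 5 (section 7.3) names the instrument as "PROMIS-29, physical function, anxiety, depression, pain interference, pain severity, fatigue, sleep disturbance, ability to participate in social roles and activities" and says of scoring: "each of the 7 domains will be scored separately, transformation in standardized t-values". Neither place states a reference population, the orientation of the scores or any recoding. The list has eight names for what the SAP calls seven domains; pain severity is the extra one and is left aside here.

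**The concern.** The list mixes two kinds of scale. Anxiety, depression, pain interference, fatigue and sleep disturbance are named for a symptom, so a high score should mean more of it. Physical function and ability to participate are named for a capacity, so a high score should mean better. One low numeric range cannot mark the same kind of patient in both.

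For the two function domains a low cut separates impaired patients from the rest. For the five symptom domains it separates patients with unusually few symptoms from everyone else, which says little about whether the treatment works differently in severe disease. In fatigue the low group may hold almost nobody, because section 4.1 requires chronic fatigue at screening. The interaction and the marginal effect promised for that group would then rest on a handful of patients or none.

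**Working it through.** **Inputs from the SAP.** Section 4.2: "a total of 66 patients (allocated in a 2:1 ratio: immunoabsorption (IA) group: 44 patients vs. sham group: 22 patients"; "a common standard deviation of 5.8" for the primary endpoint; and, for the Chalder Fatigue Scale, a mean in patients "suffering from CFS is 24.4 (with a standard deviation of 5.8) and for a healthy sample a mean value of 14.2", with a healthy SD of 4.6. **Assumptions (not in the SAP):** PROMIS T-scores have reference mean 50 and SD 10; symptom scores rise with severity; baseline scores are roughly normal, with the means and SDs shown below.

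**Step 1: reproduce the SAP's own figures.** Half-width = t(0.975, n1+n2-2) × 5.8 × √(1/n1 + 1/n2). For 44 and 22 this is 3.026 (SAP: 3.03); for 35 and 18 it is 3.377 (SAP: 3.37). Sample size, allocation and SD are therefore read correctly.

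**Step 2: expected patients on each side, symptom domains.** Below a cut: 66 × Φ((cut − mean)/SD). Sham patients are one third of the total.

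| Assumed mean | Below 30, SD 10 | Below 40, SD 10 | of which sham | Below 40, SD 8 |
|---|---|---|---|---|
| 50 | 1.5 | 10.5 | 3.5 | 7.0 |
| 55 | 0.4 | 4.4 | 1.5 | 2.0 |
| 60 | 0.1 | 1.5 | 0.5 | 0.4 |
| 65 | 0.0 | 0.4 | 0.1 | 0.1 |

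Reading 30-40 as a band does not help fatigue: the band holds 4.0, 1.4 and 0.4 patients at means of 55, 60 and 65 (SD 10).

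**Step 3: function domains, same cut.** Below 40 with SD 10: 45.6, 33.0 and 20.4 of 66 at assumed means of 35, 40 and 45. There the cut of 40 gives usable groups.

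**Step 4: rough proxy for fatigue.** Put the Chalder figures on a T metric: mean = 50 + 10 × (24.4 − 14.2)/4.6 = 72.2; SD = 10 × 5.8/4.6 = 12.6. Then Φ((40 − 72.17)/12.61) = 0.0054, so 0.35 of 66 patients and 0.12 of 22 sham patients. A cut of 30 gives 0.03 of 66.

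**Step 5: consequence for the interaction.** Half-width = 1.96 × 5.8 × √(sum of 1/n over the four cells), on the 0-33 Chalder scale, with all 66 patients and no gain from covariates.

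| Share on the small side | Half-width (points) | Chance of no sham patient there |
|---|---|---|
| 50% | 5.9 | about 0 |
| 15.9% (mean 50, cut 40) | 8.1 | 2% |
| 6.7% (mean 55, cut 40) | 11.9 | 22% |
| 2.3% (mean 60, cut 40) | 19.9 | 60% |

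The last column is (1 − share)^22.

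**Step 6: possible replacements, symptom domains (SD 10).** Above 60: 10.5, 20.4, 33.0 and 45.6 of 66 at means of 50, 55, 60 and 65. Above 70: 1.5, 4.4, 10.5 and 20.4. On the Chalder proxy for fatigue, a cut of 60 splits about 11 from 55 and a cut of 70 about 28 from 38. A median split gives about 33 and 33 (22 active and 11 sham on each side).

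**The case against.** The SAP states neither the orientation nor the T metric; both are inferred here, the first from the domain names. The wording gives a range, which could mean one cut, a band, or a value chosen per domain. The trial is described as exploratory, and sparse groups would show themselves through wide intervals. All of this stands as a limit on the claim. It does not rescue the row: no value in the range, and no band within it, gives a usable fatigue subgroup at the means considered, and if symptom scores are to be reversed the SAP does not say so.

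Three stronger readings are tempting and are not supported.

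- A reader might infer that all five symptom subgroups are nearly empty. This is shown only for fatigue. Section 4.1 excludes acute or severe psychiatric disease, including major unstable depression, so a mean near 50 for anxiety or depression is possible. A cut of 40 would then put about 10 of 66 patients on the low side, though a cut of 30 would put only 1.5 there.
- A reader might infer that the symptom groups are split in the wrong direction. A two-level split has no direction; swapping the labels only changes the sign of the interaction. The fault is a cut in the wrong tail.
- A reader might take 0.35 of 66 as a PROMIS figure. It rescales a different, bounded instrument and is only a rough proxy.

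**Conclusion.** The point holds in limited form. Followed as written, section 9.5 cuts the seven domains at opposite ends of severity and yields a fatigue subgroup that is almost empty on the low side: about 4.4, 1.5 or 0.4 of 66 patients below 40 at means of 55, 60 or 65. The interaction for the first two cases would have a 95% half-width of about 12 to 20 points on a 33-point scale, and might not be estimable at all. For the other symptom domains the low side ranges from very small to about 10 patients, depending on baseline means that the SAP does not give. The result rests on the assumed T metric, the inferred orientation and approximate normality. It concerns exploratory subgroup analyses only, so it should be corrected but does not threaten the primary analysis.

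**What to change.** In the PROMIS row of section 9.5, replace the common range with one of two specifications:

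1. One stated cut and direction per domain. Keep a low-side cut for physical function and social participation, and use a high-side cut for the five symptom domains, for example 60. A cut of 70 may again be sparse outside fatigue.
2. A baseline median split for every domain, as the same table already does for pRNFL and GCIPL, with a rule for ties. This gives about 33 patients on each side and needs no assumption about the distribution.

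In either case state the orientation of the scores and label the groups by severity in every domain, so that rows of the results table can be compared. The cost is one line of SAP wording and no new data. The drawback is several cut values under the first option, or cuts that depend on the sample under the second. The change should be made before treatment-group results are seen, so that the cut cannot be chosen after the fact.

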### 9.2 Primary analysis

For the primary outcome, the Chalder Fatigue Scale at 2 months, descriptive statistics will be presented for both treatment arms. This will include the number of participants (n), mean, standard deviation (SD), median, interquartile range (IQR), minimum, and maximum for the continuous total score. Additionally, for the categorical responses (e.g., presence/absence of fatigue), frequencies and percentages will be reported.

Confirmatory analysis of the primary outcome will be conducted based on the full analysis set. An analysis of covariance (ANCOVA) will be conducted. The dependent variable is the Chalder Fatigue Score at day 60, independent variables include baseline Chalder Fatigue Score, treatment group (intervention / control), and age at baseline. The effect estimate for the treatment variable and the corresponding 95%CI will be reported. Sensitivity analysis will be done using the PPS without imputation of missing values.

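### Section 9.5 tests effect modification only on cut versions of 14 numeric baseline measures: the seven PROMIS cuts are not determined by the text, and the others are defined but inefficient

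*SAP*

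**What the plan says.** Section 9.5 takes the models of the earlier sections, "additionally with an interaction term of the treatment group variable with the subgroup". Its stated purpose is to find indications of differential effects. It reports interaction estimates with 95% confidence intervals and marginal effects per subgroup, for the primary endpoint and the efficacy-related secondary endpoints.

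The factors cut from a numeric baseline measure are:

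- five with fixed cuts: age at 40 years, BMI at 30, disease duration at 2.5 years, Bell score at 30 and Chalder score at 20;
- seven PROMIS-29 domains, with "T-score cut offs of 30-40";
- two with median splits: pRNFL, and "Subgroups by baseline retinal ganglion cell layer (GCIPL) thickness (median split".

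Table 5 scores each PROMIS domain separately as a standardised T-value. In section 9.2 the "independent variables include baseline Chalder Fatigue Score, treatment group (intervention / control), and age at baseline", with no cut mentioned. Section 9.5 plans no interaction with an uncut moderator, and the SAP gives no power or precision for any interaction.

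**The concern.** There are two separate matters.

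**The PROMIS row is not executable.** A range can mean one cut somewhere between 30 and 40, two cuts giving three groups, or different cuts by domain. The same range serves function domains and symptom domains, and no direction is stated. Someone must settle this later, possibly after seeing data, for seven factors and every efficacy endpoint.

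**The other cuts cost precision.** With 22 sham patients, interaction estimates are already wide. Reducing a measured score to two groups discards information that the trial has collected and makes the result depend on where the cut lies. At stake is how much the subgroup section can show, not the validity of the main result.

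**Working it through.** **Inputs from the SAP.** Section 4.2: patients are "allocated in a 2:1 ratio: immunoabsorption (IA) group: 44 patients vs. sham group: 22 patients"; the precision calculation uses "a common standard deviation of 5.8 as provided for patient with CFS/ME"; the mean score for patients "suffering from CFS is 24.4 (with a standard deviation of 5.8"); 20% drop-out leaves 35 and 18.

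**Inputs assumed here, not in the SAP.** Normal moderator, linear modification, two-sided 5% test, baseline-to-outcome correlation r = 0.5, and PROMIS means and SD.

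**1. The SAP's own figure.** Half-width = t(0.975, n1+n2−2) × 5.8 × √(1/n1 + 1/n2).
- 44/22: 1.998 × 1.514 = 3.03 (SAP: 3.03).
- 35/18: 2.008 × 1.682 = 3.38 (SAP: 3.37, apparently truncated).

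**2. Count.** 5 fixed cuts + 7 PROMIS domains + 2 median splits = 14.

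**3. Precision of an interaction with a two-level factor.** With share p in one level, SE = 5.8 × √(1/(n1p) + 1/(n2p) + 1/(n1(1−p)) + 1/(n2(1−p))).
- 44/22, p = 0.5: SE = 5.8 × √(1/22 + 1/11 + 1/22 + 1/11) = 3.03; half-width about 6.05 points.
- 35/18, p = 0.5: SE = 3.36; half-width about 6.76 points.

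Each is twice the overall half-width.

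**4. Information kept by a cut**, relative to a linear interaction with a normal moderator: φ(c)² / (p(1−p)).
- Median split: 0.637, so 66 patients act like 66 × 0.637 = 42.
- Uniform moderator, median split: (1/2)² / (1/3) = 0.75.
- Four equally likely, equally spaced values (−3, −1, 1, 3), even split: 2²/5 = 0.80.

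**5. Chalder cut at 20.** Under mean 24.4 and SD 5.8, P(score ≤ 20) = Φ((20.5 − 24.4)/5.8) = 0.25 with continuity correction, and Φ((20 − 24.4)/5.8) = 0.22 without.
- Sham patients in the lower group: 22 × 0.25 = 5.5 (4.9 without the correction). After drop-out: 18 × 0.25 = 4.5.
- Information kept: about 52–54%.
- Interaction half-width with 66 patients: about 7.0–7.3 points.

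**6. Power by simulation**, r = 0.5, SD 5.8. The slope is the change in treatment effect per SD of the moderator.

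| Slope (points per SD) | 44/22 continuous | 44/22 median split | 35/18 continuous | 35/18 median split |
|---|---|---|---|---|
| 1 | 12% | 9% | 11% | 8% |
| 2 | 30% | 20% | 26% | 17% |
| 3 | 57% | 37% | 49% | 32% |
| 4 | 80% | 57% | not tabulated | not tabulated |

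A 25/75 split with 44/22 gives about 31% at slope 3 and 50% at slope 4. Without the gain from the baseline covariate (residual SD 5.8), power is 30 / 52 / 79% continuous against about 21 / 35 / 56% median split at slopes 2.3 / 3.3 / 4.5.

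To read the slopes: median halves of a normal moderator differ by 2√(2/π) = 1.6 SD. Slope 3 therefore means a 4.8-point difference in effect between halves, and slope 4 means 6.4 points.

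**7. PROMIS.** Share of patients below the cut, assuming SD 8:

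| Assumed mean T | Cut at 30 | Cut at 40 |
|---|---|---|
| 35 | 27% | 73% |
| 40 | 11% | 50% |
| 45 | 3% | 27% |
| 50 | 1% | 11% |

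The group sizes depend heavily on the choice that the text leaves open.

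**The case against.** Most of the section is precise. The median splits and the cuts for age, BMI, disease duration, Bell and Chalder are fully specified and leave nothing to choose after the data are seen. A reader might infer that they are errors. They are not: categorising is a legitimate, if inefficient, choice for analyses that seek only indications.

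The power loss also varies. Slopes of 3 or 4 imply differences between halves (4.8 and 6.4 points) larger than the 4.5-point treatment effect cited in section 4.2 from an earlier trial. At slopes of 1 or 2 both approaches are weak and the gap is 3 to 10 percentage points. The loss shrinks for bounded or few-valued moderators. Bell is limited to 20–50 at entry (section 4.1) and would have four values if scored in tens. With a true threshold at the median the split is better: 31% versus 27% for a 4.5-point step, and 48% versus 39% for 6 points. Section 9.5 also sets no significance rule for interactions, so power serves here only as a measure of precision.

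These points stand and limit the size of the concern. None of them settles the PROMIS row.

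Two further inferences fail. Interacting a category while age and baseline Chalder stay in the model as covariates is not a defect, because the adjustment is retained. Nor does a T-score of 35 necessarily lack a group: with two cuts it would fall in the middle band. The text is ambiguous rather than silent.

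**Conclusion.** The point holds as a low-severity improvement with one real gap in specification.

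- **PROMIS:** seven of the 14 factors cannot be formed from section 9.5 as written. This rests on the text alone and needs no modelling assumption.
- **The other seven:** defined but inefficient. The median-split loss is about 36% of the information for a normal moderator and 25% for a uniform one, given linear modification. The power cost runs from about 3 points (slope 1) to 23 points (slope 4) with 44/22. The Chalder cut would leave about 5 to 6 sham patients in the lower group if the cited mean and SD apply.

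The documents do not support reading this as a threat to the primary analysis or its error rate. Section 9.2 does not depend on the subgroup definitions.

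**What to change.** In section 9.5, for each numeric moderator (optional for Bell, given its few levels at entry):

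1. Make the main interaction analysis treatment × moderator on the original scale, with the moderator's main effect. Report the slope and its 95% confidence interval.
2. Give marginal treatment effects at the 25th and 75th percentiles of the moderator.
3. Keep the stated categories for display and as a check of linearity.
4. For PROMIS, use the T-score continuously. Replace the 30–40 range with one exact cut and direction per domain, fixed before unblinding, for the display.

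This changes SAP wording only. The data are the same and the planned emmeans package can give the marginal effects. The cost is an assumption of linear modification, which the categorical display can check, and slightly more analysis work.
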